Population: 10,449 patients aged 16-35 years in CPRD with TASD and two years follow up.

WP1: Internal and external validation of shoulder dislocation coding and treatments within a routinely collected dataset (CPRD).

WP2: Propensity score-matched cohort study using linked CPRD and HES. All events and outcomes will be collected using a pre-agreed list of READ CODES (CPRD) and OPCS 4.7 CODES (HES).

Exclusions: Surgery after more than one dislocation; instability treated with a rotator cuff repair or fracture surgery.

Intervention: Surgical repair within 6 months of first time T ASD.

Control: non-surgical intervention.

Outcomes: Rate of re-dislocation, identified by codes in CPRD for 2 years after either treatment.

Sample size: 3065 with 656 expected total number of re-dislocations (90% power, 5% significance).

Statistical analysis: Propensity scores, Cox regression modelling and Rosenbaum bounds sensitivity analysis for *Surgical versus non-surgical intervention on re-dislocation*. Multiple imputation methods, survival models and fractional polynomials for *Predictors of recurrent dislocations*.

C. Objectives, Specific Aims and Rationale

Aim 1. To study the association between surgical treatment (compared to no surgery) and recurrence rates following a first episode of traumatic anterior shoulder dislocation (T ASD) amongst young adults. **Aim 2.** To identify clinical predictors of further recurrent dislocations in young adults with traumatic anterior shoulder dislocation stratified by surgery and no surgery.

Objectives: Following the HTA commissioning brief, we plan to use routinely collected observational datasets (Clinical Practice Research Datalink (CPRD) and Hospital Episodes Statistics (HES)) to answer the research questions above. The size of routinely collected data in UK primary care (CPRD) and secondary care (HES) offers rapid observational data to uncertainties about treatments in an affordable and generalisable manner. We have planned a propensity score-matched cohort study, with the intention to minimise confounding. Propensity score matching is considered one of the best methods available to approximate to any results obtained from randomised controlled trials. To ensure further value for money and to confirm the ability of these datasets to answer this very specific commissioned question, we plan a two stage approach through Work Packages 1 and 2.

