Using data from a Cochrane systematic review comparing surgical to non-surgical treatment for acute T ASD [6]; from the pooled results 3/58 patients in the surgical arm had subsequent further surgery (5.17%) compared to 17/61 in the non-surgical arm (27.9%) at a minimum follow up of 2-years (Risk Ratio 0.22, 95% CI 0.08 to 0.64). The large effect size is set in the context of the pooled results of 3 RCTs with uncertainty around the true size of the effect outside of a clinical trial setting in routine general practice. Conservatively, we would look to detect a smaller difference in subsequent surgery within 2-years of 25% in the non-surgical group, compared to 20% in the surgical group (an absolute difference of 5%). A 2-sided log rank test for equality of survival curves, with 90% power at 5% significance level (alpha), where outcome is time to re-dislocation, with an anticipated 25% re-dislocation rate in the non-surgical control group compared to a 20% in the surgical group (equivalent to a hazard ratio of 0.78), allowing for 10% loss to follow up and assuming equal group sizes, we require a total sample size of 3065 with 656 expected total of re-dislocations. There are 26,534 patients in CPRD with recurrent anterior shoulder dislocations, and at least 10,449 of these patients will be aged 16-35 years with T ASD [7]. The study will therefore be adequately powered. ***See flow diagram in appendix for estimation of numbers.***

H. Data Linkage Required (if applicable)

Data linkage and data management for our proposed study involves 2 different data sources (CPRD and HES). They need to be linked to answer the aims of WP2 as stated above. We have therefore included co-applicants with extensive experience in the use of linked datasets. The data management needed to produce a final working dataset will be carried out by a senior data manager at Oxford with expertise in such procedures. Under supervision from the application team, the data manager will develop ad-hoc code in Python and SQL to produce a dataset that can be analysed using standard statistical packages such as Stata.

I. Study Population

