This commissioned call is directed at 'younger adults'. From age 40 years onwards instability and dislocation is associated with rotator cuff tears and the pathology and outcomes are different. Rotator cuff tears are highly rare below age 35 years and so our young target population will be patients aged 16-35 years in CPRD with a first time T ASD who underwent stabilisation surgery within 6 months of their first dislocation. We require a total sample size of 3065 with 656 expected total of re-dislocations. There are 26,534 patients in CPRD with recurrent anterior shoulder dislocations, and at least 10,449 of these patients will be aged 16-35 years with T ASD [7].

Inclusion criteria: Patients aged 16-35 years of age with a first time traumatic anterior dislocation (T ASD); patients that can be linked by CPRD and HES; minimum two year follow up period in CPRD.

Exclusion criteria: Surgery after more than one dislocation; instability treated with a rotator cuff repair or fracture surgery. We will also exclude:

- Patients aged 16-35 years with first time T ASD who cannot be linked by CPRD-HES
- Patients with less than two year follow up in CPRD
- Surgery after more than one T ASD
- Instability treated with rotator cuff repair surgery or fracture surgery.

J. Selection of comparison group(s) or controls

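### Requiring two years of actual follow-up makes eligibility depend on the future and contradicts the 10% loss to follow-up built into the sample size

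*Protocol*

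**What the plan says.** Section I (Study Population) states the rule twice: as an inclusion criterion, "minimum two year follow up period in CPRD", and as an exclusion, "Patients with less than two year follow up in CPRD". Section F, under Main study (WP2), counts the two years from the first dislocation code. Section B describes the pool of 10,449 patients as having two years of follow-up. Sections C, G and I give the same 10,449 without mentioning a follow-up filter.

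Section G sizes the study with "A 2-sided log rank test for equality of survival curves" at 90% power and 5% significance. It takes an "anticipated 25% re-dislocation rate in the non-surgical control group compared to a 20% in the surgical group", "equivalent to a hazard ratio of 0.78", with equal groups and "allowing for 10% loss to follow up". The result is 3,065 patients and 656 re-dislocations.

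Section L defines the primary outcome as time from first dislocation to re-dislocation within two years, analysed by Cox regression on matched sets with Kaplan-Meier plots to two years. Section B instead says that outcomes are identified "for 2 years after either treatment".

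The protocol gives no reason for the follow-up criterion, does not reconcile it with the 10% allowance, and plans no analysis that keeps patients with shorter follow-up.

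**The concern.** The criterion is worded as actual follow-up, not as a calendar limit on the index date. Whether a patient belongs to the cohort is therefore settled only two years after the first dislocation. Someone who re-dislocates at month 5 and changes practice at month 14 is removed together with the event. Section L takes care to avoid immortal time in the definition of surgery, but the eligibility rule conditions on the future by another route and is not discussed.

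The planned Cox and Kaplan-Meier methods do not need this restriction, because they use each patient's time up to leaving. Two things are at stake. One is whether the two-year risks, and possibly the comparison, describe all first-time dislocators or only those who stay. The other is whether the sample size describes the cohort that will be analysed.

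**Working it through.** **Inputs (Section G):** two-year risks of 25% and 20%, two-sided 5%, 90% power, 1:1 allocation, 10% loss. The unrounded hazard ratio is ln(0.80)/ln(0.75) = 0.7757, with log 0.254 in absolute value. The mean risk is 0.225.

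**Step 1: events.** Schoenfeld: 4 × (1.960 + 1.282)² / 0.254² gives 652. Freedman gives 659. The stated 656 lies between them.

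**Step 2: how the 10% was used.** Treat loss as exponential censoring that reaches 10% by two years, competing with exponential event times. The probability of an observed event in an arm with two-year survival S is

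P = λ/(λ + γ) × (1 − 0.9 × S), with λ = −ln(S)/2 and γ = −ln(0.9)/2 = 0.0527.

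- Control: 0.1438/0.1965 × (1 − 0.675) = 0.2379
- Surgical: 0.1116/0.1642 × (1 − 0.720) = 0.1902
- Mean: 0.2140 (0.21404 before rounding)

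656/0.21404 = 3,065, which is the stated figure. The alternatives for the same 656 events do not match:

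| Handling of loss | Total N |
|---|---|
| Exponential censoring, 10% by two years | 3,065 |
| No loss: 656/0.225 | 2,916 |
| Inflate by 1/(1 − 0.10) | 3,240 |
| Inflate by 1.10 | 3,207 |

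Section G does not use the word censoring, but of these conventions only censoring returns its number.

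**Step 3: the exclusion as written.** Nobody in the cohort can be lost within two years of the first dislocation, which is the outcome window in Section L. The row without loss then applies: 656 events need about 2,916 patients. If 3,065 eligible patients are analysed, events are 3,065 × 0.225 = 690, and power is Φ(√690 × 0.254/2 − 1.96) = 91.6%. For 656 events the same formula gives 90.2%.

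**Step 4: effect of the selection (retention rates assumed).** Suppose 95% of re-dislocators and 85% of other patients stay registered for two years, in both arms.

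- Control: 0.25 × 0.95 / (0.25 × 0.95 + 0.75 × 0.85) = 0.2375/0.8750 = 27.1% instead of 25%
- Surgical: 0.20 × 0.95 / (0.20 × 0.95 + 0.80 × 0.85) = 0.19/0.87 = 21.8% instead of 20%
- Hazard ratio among those who stay: ln(1 − 0.2184)/ln(1 − 0.2714) = 0.778, against 0.776

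The absolute risks move by about two percentage points and the hazard ratio hardly at all. If leaving is unrelated to both treatment and re-dislocation, neither moves and the only cost is precision.

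**The case against.** **Power.** A reader might infer that the exclusion makes the study miss its 656 events. Removing 10% from 3,065 leaves 2,759 patients, about 621 events and 88.6% power. That holds only if 3,065 counts patients before the eligibility criteria are applied. It is the required analysis sample, the criteria act on the pool, and Section B describes the pool as already having two years of follow-up. This objection stands, and no power loss is claimed.

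**Bias.** A reader might take the move from 25% to 27.1% as bias in the treatment effect. Step 4 shows that the same retention pattern in both arms leaves the hazard ratio where it was. Biasing the comparison needs retention patterns that differ by arm, and the protocol has no retention data. This stands too.

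**Information gained.** Section L stratifies the Cox model on matched sets. Once one member of a 1:1 pair is censored, later events in the other add nothing to the partial likelihood. Keeping early leavers therefore recovers less information than an unstratified log-rank calculation suggests.

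**Time origin.** A patient operated on at six months who just meets the criterion has only 18 months of data after surgery. It is tempting to blame the exclusion. The cause is a separate conflict, between Section B (two years after treatment) and Sections F and L (two years from first dislocation), and dropping the criterion would not resolve it.

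**Is it needed elsewhere?** Section F also plans a cost description, for which truncated records are awkward, and it schedules an updated analysis plan before WP2. Both are fair points about how to make the change. Neither explains why a time-to-event analysis should select on later follow-up.

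**Conclusion.** The point holds in limited form. Sections F and I select on two years of actual follow-up after time zero, and this contradicts Section G, whose 3,065 rests on 10% being lost before two years and censored. Under the exclusion the allowance is redundant and about 2,916 patients would give the 656 events, so the stated number is, if anything, slightly generous.

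The real cost is selection. Re-dislocations among early leavers are dropped, and the absolute two-year risks are distorted if staying registered is related to re-dislocation. The shift of about two percentage points rests entirely on the assumed 95% and 85% retention. The size and direction of any bias in the hazard ratio cannot be worked out from the protocol, which gives neither a rate of early leaving nor its relation to treatment or outcome.

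The protocol should be changed because the selection is avoidable and unexplained, not because harm to the comparison has been shown.

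**What to change.** - For the WP2 re-dislocation analyses, replace the two-year actual follow-up criterion in Sections B, F (Main study) and I. Require either any follow-up after the index date, or potential follow-up (index date at least two years before the end of data).
- Censor at deregistration, death, last data collection or two years from the stated time origin, whichever comes first.
- Keep the 10% allowance in Section G, which then agrees with the eligibility rule.
- Report the two-year-complete cohort as a sensitivity analysis and, if needed, use it for the cost description in Section F.
- Separately, reconcile the time origin between Section B (two years after treatment) and Sections F and L (two years from first dislocation).

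The cost is small: this is a retrospective database study, and the change needs only new wording and routine censoring dates. The updated analysis plan due before WP2 is a natural place for it. Two downsides remain. Censoring still assumes that leaving is non-informative, and a cost analysis on the wider cohort must deal with truncated records.

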The ***Intervention group*** will be patients in CPRD with first time T ASD who underwent shoulder stabilisation surgery after their first dislocation (early surgical repair in this NHS context will mean 'a decision to treat surgically after the first T ASD' and receiving surgery within 6 months). This means linking HES data to CPRD data in such a way that a HES surgical OPCS 4.7 code is seen to occur after a single first dislocation code in CPRD (without further dislocation codes) before that surgical date. The timelines between first dislocation codes and OPCS 4.7 codes will be recorded. The ***Control group***. While the most desirable control group would be physiotherapy, it is possible that WP1 will reveal that free text notes and referral codes on physiotherapy will be lacking and not reliable. If this is the case then conservative care will be defined as 'non surgical intervention' with no linked OPCS 4.7 surgical shoulder codes producing a control cohort of patients whose first time shoulder dislocation has been treated non-operatively. If however free text entries and referral codes for physiotherapy are reliably present in CPRD then conservative care will be physiotherapy identified by physiotherapy referral codes after a first time T ASD code. Any subsequent dislocation codes or OPCS 4.7 surgery code will be recorded.

K. Exposures, Outcomes and Covariates

As part of this application, we have performed a consensus survey of specialist shoulder surgeons and shoulder physiotherapists who are all members of the British Elbow and Shoulder Society. Saturation point and a list of predictors was reached rapidly and this list is tabulated in Appendix E and highlights the risk factors (and covariates) deemed most important. It is unlikely that all of these will be available from routinely collected national datasets but our study design will allow us to confirm through WP1 those factors that are reliably collected and that can be used for full analysis in WP2.

L. Data/ Statistical analysis

The association of surgical versus non-surgical intervention on subsequent re-dislocation within 2-years. The primary outcome of interest is the time from a first time traumatic anterior dislocation to subsequent re-dislocation within 2-years. The exposure of interest is whether or not a patient received shoulder surgery. In randomized controlled trials each person has

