This project was funded by the National Institute for Health Research Health Technology Assessment (project number 14/160/01).

The views and opinions expressed therein are those of the authors and do not necessarily reflect those of the HTA, NIHR, NHS or the Department of Health.

an equal probability of being in a treatment or control group. Observational study designs are limited by an inherent imbalance of both known and unknown confounders making some patients more likely to receive surgery than others. As the type of surgery received is not randomly allocated in our study, confounding by indication will be accounted for by using propensity score matching methods. Use of these methods for the assessment of causality in epidemiological studies has been previously described[1]. The propensity score represents the probability that a patient received the intervention (surgery). A logistic equation is fitted where the outcome is surgical intervention versus non-surgical; and any covariates are introduced as potential confounders of subsequent dislocation. We have already identified an expert consensus list of all potential confounders of interest (Appendix E)

Propensity scores are used to match each patient receiving surgery to comparable non-surgical controls using a caliper width of 0.2 standard deviations of the logit of the propensity score[2]. This is a standard method for minimizing confounding by indication, which not only balances observed baseline characteristics in both surgical and non-surgical groups, but also eliminates surgical patients with no comparable controls[3].

Immortal time bias is a common issue in epidemiological studies, where the event of interest cannot occur for a certain time span. In the case of this proposed study immortal time bias would occur due to the definition of exposure, where in the time from first dislocation till receipt of surgery those in the 'surgical arm' cannot have the outcome by design otherwise they would have been classified as non-surgical. To avoid the problem of immortal time bias, we will use time varying exposures, where in a survival analysis the time period previous to the index date of surgery is reclassified as non-surgical for those in the surgical intervention group.

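### Excluding patients operated on after a re-dislocation selects on events after the outcome, can bias the comparison against early surgery, and contradicts the analysis section

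*Protocol*

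**What the plan says.** - **Section I, Study Population**, excludes "Surgery after more than one dislocation; instability treated with a rotator cuff repair or fracture surgery", and its bullet list repeats the first part as "Surgery after more than one T ASD". The Technical Summary (section B) carries the same exclusion. None of these places sets a time limit or confines the rule to the intervention group.
- **Sections F and J** define the intervention group by a surgical code that follows a single dislocation code, with no further dislocation code before the operation, and surgery within 6 months.
- **Sections F and J** prefer a physiotherapy control group. If physiotherapy coding proves unreliable, the fallback is a non-surgical group "with no linked OPCS 4.7 surgical shoulder codes producing a control cohort of patients", again without a time window. The paragraph ends: "Any subsequent dislocation codes or OPCS 4.7 surgery code will be recorded".
- **Section L** defines the primary outcome as "the time from a first time traumatic anterior dislocation to subsequent re-dislocation within 2-years". In explaining immortal time, it says that before the operation the surgical patients "cannot have the outcome by design otherwise they would have been classified as non-surgical".

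**The concern.** Whether a patient treated without surgery stays in the study depends on what happens after that patient has reached the outcome. A control who re-dislocates and is not operated on stays and counts as an event. A control who re-dislocates and is then operated on is excluded under section I and, under the fallback definition, is also barred from the control group. Section L, by contrast, would classify that patient as non-surgical.

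The loss is selective because it takes events, not a random sample of controls. If it takes a larger share of events from the control group than from the surgical group, the control re-dislocation rate is understated and early surgery looks less effective than it is. At stake is the direction of the primary comparison.

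The planned analyses do not reach this. Matching and the practice frailty term act on patients already selected. Rosenbaum bounds address unmeasured confounding. The sensitivity analysis at the end of section L drops early re-dislocations after surgery, which are events in the other group.

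**Working it through.** **Inputs from section G.** "A 2-sided log rank test for equality of survival curves", 90% power, 5% significance, 2-year re-dislocation 25% (non-surgical) versus 20% (surgical), hazard ratio 0.78, 10% loss, equal groups, 3065 patients and 656 events.

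**Reproducing the plan.**
- HR = ln(0.80)/ln(0.75) = 0.776.
- Events needed: 652 (Schoenfeld) or 659 (Freedman), against 656 stated.
- With 10% loss as exponential censoring, the event probability per group is λ/(λ+w) × (1 − exp(−(λ+w))), where λ = −ln(1−p) and w = −ln(0.90). The mean over the two groups is 0.21404, and 656/0.21404 = 3065.
- Power at 656 events = Φ(√656 × |ln 0.776|/2 − 1.96) = 0.90.

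The plan's figures stand, on the premise that every control re-dislocation is counted.

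**Effect of the exclusion.** Let f be the share of control re-dislocators removed through later surgery and g the same share in the surgical group (re-dislocation followed by revision). Both are assumptions.

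Observed risk = p(1 − f)/(1 − p·f) for controls, and likewise with g for surgery. Observed HR = ln(1 − surgical risk)/ln(1 − control risk). Power uses the Schoenfeld formula, with 3065 patients and the same loss.

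| f | g | Control risk | Surgical risk | HR | Events | Power |
|---|---|---|---|---|---|---|
| 0 | 0 | 25.0% | 20.0% | 0.776 | 656 | 0.90 |
| 0.10 | 0 | 23.1% | 20.0% | 0.851 | 628 | 0.53 |
| 0.25 | 0 | 20.0% | 20.0% | 1.000 | 583 | none (null) |
| 0.50 | 0 | 14.3% | 20.0% | 1.448 | 500 | about 0.98, wrong direction |
| 0.25 | 0.10 | 20.0% | 18.4% | 0.909 | 559 | 0.20 |
| 0.50 | 0.10 | 14.3% | 18.4% | 1.317 | 476 | 0.85, wrong direction |
| 0.50 | 0.25 | 14.3% | 15.8% | 1.115 | 438 | 0.20, wrong direction |
| 0.50 | 0.50 | 14.3% | 11.1% | 0.764 | 370 | 0.73 |

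At f = g = 0.10 and f = g = 0.25 the HR is 0.774 and 0.770.

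**Break-even.** Removing a share f of events multiplies a group's odds by (1 − f). The planned odds are 0.25/0.75 = 1/3 and 0.20/0.80 = 1/4, so the observed risks are equal when (1 − f)/(1 − g) = 0.75. That gives f = 0.25 at g = 0, f = 0.325 at g = 0.10 and f = 0.4375 at g = 0.25. At the pooled trial rates in section G (17/61 versus 3/58, which are subsequent-surgery rates and only a proxy), the odds are 17/44 and 3/55. Break-even at g = 0 is then f = 1 − (3/55)/(17/44) = 0.86.

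**The case against.** **The bias need not run one way.** A reader might infer that the exclusion can only hurt surgery. The criterion as written also covers an early-surgery patient who re-dislocates and has a revision. With equal shares removed, the hazard ratio barely moves. This stands: the g = 0 rows are the worst case at each f. A related group works the other way. Patients operated on after 6 months without recurrence fit neither the intervention definition nor the fallback control definition. They are event-free up to that operation, so losing them tends to raise the observed control rate.

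**The size of f is not documented.** A reader might take "17/61 in the non-surgical arm (27.9%) at a minimum follow up of 2-years" as evidence that f is large, because it is about as big as the assumed 25% re-dislocation rate. That does not follow. The 27.9% is later surgery among trial patients. Section G uses 25% first for subsequent surgery and then for re-dislocation, so the near-equality comes from that change of endpoint. It says nothing about the share of re-dislocators who are operated on.

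**Immortal time.** One might add that the exclusion also undermines the time-varying exposure, because event-free time before surgery is credited to non-surgery while re-dislocations before surgery are dropped. In a Cox model stratified on matched sets, both members of a pair are unexposed before the surgery date, so events in that period carry no information on the treatment effect. No extra bias should be claimed.

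**The control definition is provisional.** The rule requiring no surgical code is only the fallback, and section F provides for an updated analysis plan before WP2. This stands too. But the population exclusion in section I applies whichever control definition is chosen, so the physiotherapy option does not remove the problem.

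**Conclusion.** The point holds in limited form. As written, eligibility depends on surgery after the outcome, sections I and L contradict each other, and no planned analysis makes good the loss. The exclusion is not needed to keep the surgical group clean, because section J already requires a single dislocation code before the operation.

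The direction and size depend on two shares that the documents do not give. If f exceeds g, which is plausible but not documented, the bias is against surgery. At the planned 25% versus 20% with no revisions removed, losing a tenth of control re-dislocators takes power from about 90% to 53%, a quarter gives a null result, and half gives a hazard ratio of 1.45. Removing revisions as well softens this. The low break-even also reflects the deliberately small planned difference: at the pooled trial rates it would be about 0.86. The power figures are for the plan's log-rank calculation with 3065 patients retained. They are not for the pair-stratified model.

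Reversal is therefore possible but not shown to be likely. The rule should still be corrected before the cohort is extracted, because it can change the primary conclusion and costs little to change.

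**What to change.** 1. Delete surgery after more than one dislocation as an exclusion from the study population (sections B and I). Use it only to define who counts as early surgery, as section J already does.
2. Keep patients operated on after a re-dislocation in the non-surgical group, with the re-dislocation counted as their event.
3. Keep early-surgery patients who re-dislocate and have a revision in the surgical group, with that re-dislocation counted.
4. Replace the fallback rule requiring no surgical code at any time (sections F and J) with one that does not depend on surgery after the outcome.
5. Keep patients operated on after 6 months without recurrence as non-surgical up to that operation, and check in a sensitivity analysis whether censoring there is informative.
6. Reconcile sections B, F, I, J and L.

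The cost is revised wording and a changed extraction rule. No new data are needed, since sections F and J already provide for recording later dislocation and surgery codes. The updated analysis plan due before WP2 is a natural place to make the change.
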